5. STUDY INTERVENTIONS

5.1 Interventions, Administration, and Duration

Standard and Expanded Visit Groups

Subjects will be randomized to receive either a "standard visit" or an "expanded visit" with a study provider. The standard visit is based on a high quality, empathic, conventional primary care encounter. The expanded visit is based on an integrative medicine consultation. Both visits are based on a script of questions and statements to the

Tool Revision History

Version: 11.0

Version Date: 5.8.2020

patient/subject (see Appendix E). The standard visit script includes questions about GERD history, symptoms, prior evaluation and treatments, and past medical history as well as a brief physical exam. The expanded visit script includes the same questions as the standard visit script plus additional questions that inquire about the modalities of their GI symptoms (e.g., nature of the reflux taste, sensation of heartburn pain and/or abdominal fullness, time of day better/worse), details about non-GI symptoms, quality of sleep, the effect of the weather on symptoms, food cravings and aversions, menstrual flow, fears/phobias, and overall temperament. In this way, the expanded visit tries to understand the patient's/subject's constitution in a way that many systems of integrative medicine attempt to do. To reduce the potential for introducing bias by using the words "standard" and "expanded", the visit templates that they study providers will follow will simply refer to the number of questions to be asked on the template (e.g., 6 Question Template).

In our pilot study [61] we did not limit the amount of time spent with the study subject. On average, the standard visit lasted 18 minutes (range 11-32 minutes) and the expanded visit lasted 42 minutes (range 23-74 minutes). The study providers will be instructed to maintain equal empathy in both groups (e.g., kind and friendly manner, maintained eye contact, active listening and repeating back the patient's words, expressions of empathy). Thus, the main differences between the visits will be the length of time spent with the subject and the additional questions that are asked.

Each study provider will participate in an orientation session to learn how to deliver the standard and expanded visit interventions. Providers will be explicitly instructed not to offer specific GERD treatment advice – either pharmacologic or non-pharmacologic. The study PI will review video recordings of the interactions to offer feedback to study providers and ensure protocol fidelity. As each study provider finishes his/her portion of the study, the PI will interview them to understand their experiences of the study, the two visit types, and their views on the doctor-patient relationship.

We do not anticipate any adverse effects as a result of this intervention.

5.2 Handling of Study Interventions

To minimize potential bias that could affect study staff interactions with subjects, the study provider will open an envelope indicating which visit type he or she is to deliver immediately before conducting the study visit and will receive the appropriate study visit script. At the time of consent, study subjects will not be informed about the two different interview types or that part of the study involves testing the effect of the doctor-patient interaction on response to treatment. Concealment of these aspects of the study protocol is essential to maintaining the validity of the study as data suggests that patients responses change when they know that the doctor-patient interaction is being studied [66,67]. The study PI, or another study team physician, will notify subjects at their follow-up study visit, after the exit interview, that there were two possible types of physician visits, that this aspect of the study was concealed from them initially, and of the rationale for doing so. A script outlining this planned debriefing is present in Appendix G. We believe that this intervention is minimal risk and that our plan meets the federal criteria for permitting alteration of some elements of informed consent [69].

5.3 Concomitant Interventions

5.3.1 Allowed Interventions

Subjects are permitted to remain on all baseline medications, over-the-counter products, and dietary supplements, including those used to treat GERD symptoms (e.g., antacids, H2 receptor blockers, and proton pump inhibitors) during the study. We will request that they not change doses of medications used to treat GERD symptoms during the two weeks that they are enrolled in the study.

5.3.2 Required Interventions

None.

5.3.3 Prohibited Interventions

Subjects may not have consumed more than 15 doses of NSAIDS within the prior 30 days (or more than 8 doses during the 2 week study period. Aspirin at doses of 325 mg or less daily is permitted.

We will ask subjects not to change their GERD treatment regimen during the study. This will be monitored via the daily symptom diary.

5.4 Adherence Assessment

Subject adherence is defined by subjects completing at least 12 out of 14 days of their daily symptom diary during the two week study period. Adherence will be assessed when subjects return their symptom diaries at their follow-up visit. For subjects who return incomplete symptom diaries, average daily symptom severity for the days completed will be calculated. If there is insufficient data to make this calculation, we will assume that symptoms are unchanged from baseline.

Tool Revision History

Version: 11.0

Version Date: 5.8.2020

6. STUDY PROCEDURE**6.1 Schedule of Evaluations for Subjects/Patients**

Assessment	Telephone Screening: (Day -30 to -7)	Baseline, Enrollment, Randomization: Visit 1 (Day 0)	Post Intervention: Visit 1 (Day 0)	Follow-up: Visit 2 (Day 13-18)
Prescreen Form	X	X		
GERD Daily Symptom Diary Reviewed		X		X
Informed Consent Form		X		
Current Medication List		X		X
Height and weight		X		
Blood draw		X	X	X
Demographics & Health Behaviors		X		
GERD-Health Related Quality of Life Questionnaire (GERD-HRQL)		X		X
NIH Patient Reported Outcomes Measurement Information System (PROMIS) GERD		X		X
Gastrointestinal Symptom Rating Scale (GSRS)		X		X
Perceived Stress Scale-10 (PSS-10)		X		X
Current Stress Question		X	X	X
NEO Five Factor Inventory (NEO-FFI)		X		
Randomization		X		
HRV, respiratory rate, skin temperature, and GSR		X		
Video recording		X		
Study visit		X		
Consultation And Relational Empathy questionnaire (CARE)			X	
HEAL Patient-Provider Connection			X	
Adverse Events				X
Qualitative Interview				X
Debriefing				X

Tool Revision History

Version: 11.0

Version Date: 5.8.2020

Schedule of Evaluations for Providers

Assessment	Enrollment	Prior to each subject/patient encounter
Informed Consent Form	X	
Interpersonal Reactivity Index (IRI)	X	
NEO-FFI	X	
Demographics	X	
Intervention Training	X	
PSS-10		X
Current Stress Question		X
Fatigue Scale		X
Interview at completion of study		

6.2 Description of Evaluations

6.2.1 Telephone Screening (Day -30 to -7)

A standardized form will be used to assess the potential subject's eligibility for the study. See Appendix B.

6.2.2 Enrollment, Baseline, and Randomization (Visit 1, Day 0)

Potential subjects will be rescreened using the pre-screen form by a study physician. The study physician will also review the baseline symptom diary to ensure that the individual is symptomatic enough to enroll. If the individual is eligible to participate in the study, they will be given a copy of the consent form to review.

Consenting Procedure

Written informed consent will be obtained by a study team physician (see also section 4.3). The subject will be given adequate time to read the consent form, and any questions the subject has will be answered. The study team physician will confirm that the subject understands that he/she will be connected to physiologic monitors during the visit and that the visit will be video recorded. The subject will also have the opportunity to choose whether or not to consent to blood draws as part of the study which will involve two blood draws at the first visit and one blood draw at the second visit. The subject will receive a copy of the consent form and the original signed copy will be kept in a study binder. If the subject agrees to participate and signs the informed consent form, they will be considered "enrolled".

Study providers will be consented by the study PI, following a similar process, using a different written informed consent form.

Baseline Assessments

Evaluations for Study participants/patients:

- Current medication List – will be pulled from Epic and verified with the patient by a study team physician.
- Height and weight – will be obtained by a CRC nurse or study team member.
- Blood draw (optional) – 10 mL of blood will be obtained by a research nurse in the CRC or other appropriate clinician. Blood will be processed to obtain RNA, DNA, and plasma then frozen at -80°C for later omics analyses.
- Demographics and health behaviors – will assess things such as age, gender, race/ethnicity, smoking status, alcohol & caffeine use (see Appendix D)
- Baseline Symptom Diary – 7 day diary indicating the frequency and severity of 9 different GERD and dyspepsia-related symptoms on a 5 point scale as well as any medications, supplements, or other products used to help manage symptoms. The first 3 symptoms (daytime heartburn, nighttime heartburn, and acid reflux) will be used to assess severity of GERD symptoms.

Tool Revision History

Version: 11.0

Version Date: 5.8.2020

- GERD-HRQL - a validated 11 item scale for assessing the impact of GERD symptoms on health-related quality of life [70].
- NIH PROMIS GERD scale – a validated 13 item instrument assessing frequency and severity of GERD symptoms over a 7 day recall period [26].
- GSRS: The Gastrointestinal Symptom Rating Scale is a validated 15 item instrument for measuring the severity of gastrointestinal symptoms [71]. It contains 5 subscales: abdominal pain, reflux syndrome, diarrhea syndrome, indigestion syndrome, and constipation syndrome.
- Current Stress Question – 1 item self-report measure of current stress level on a scale of 0 (no stress) to 10 (extreme stress).
- Perceived Stress Scale (PSS) – a widely used 10 item measure of perceived stress that has been shown to correlate with a variety of different health outcomes [72]. We have adapted the originally validated measure to ask about stress over the past week (7 days), rather than the past month, to better fit the timeframe of the study. We have used this timeframe in other studies.
- NEO Five Factor Inventory (NEO-FFI) – a validated 60-item instrument that measures five major dimensions of personality: extraversion, neuroticism, agreeableness, conscientiousness, and openness to experience [73]. Some dimensions have been associated with response to enhanced patient-provider interactions in others studies [74].
- Physiologic Measures and Video Recording: During the intervention we will measure HRV, respiratory rate, skin temperature, and GSR in both study patients and study providers. The study visit will also be video recorded.

Evaluations for Study providers:

- Interpersonal Reactivity Index (IRI) — a validated 28 item self-assessment of cognitive and affective components of empathy [75].
- NEO Five Factor Inventory (NEO-FFI) – a validated 60-item instrument that measures five major dimensions of personality: extraversion, neuroticism, agreeableness, conscientiousness, and openness to experience [73]. Some dimensions have been associated with response to enhanced patient-provider interactions in others studies [74].
- Demographics and practice– will assess things such as age, gender, race/ethnicity, and clinical experience (see Appendix D)
- Current Stress Question – 1 item self-report measure of current stress level on a scale of 0 (no stress) to 10 (extreme stress). Study providers will complete this question immediately prior to each study subject visit.
- Perceived Stress Scale (PSS) – a widely used 10 item measure of perceived stress that has been shown to correlate with a variety of different health outcomes [72]. Study providers will complete this questionnaire immediately prior to each study subject visit.

Tool Revision History

Version: 11.0

Version Date: 5.8.2020

- Fatigue Scale – 1 item self-report measure of the current fatigue level on a scale of 0 (no fatigue) to 10 (extreme fatigue). Study providers will complete this question immediately prior to each study subject visit.

Randomization

Subjects will be randomized on the day of their baseline visit (Visit 1), following consent, to receive either the standard or expanded visit with the particular provided that they are scheduled to see that day. We will stratify randomization by provider so that each provider does the same proportion of standard and expanded visits. Randomization will occur after subjects have completed their optional first blood draw and baseline questionnaires, immediately prior to the study visit. Study providers will open an envelope instructing them which study visit intervention to deliver.

6.2.3 Blinding

This is a single-blinded study. Subjects will be unaware of the possibility for two different types of study visits. Study providers and staff will be aware of the study intervention delivered, but only immediately prior to the study visit to decrease the potential for introducing bias in how study staff interact with subjects during recruitment and consent. Subjects will be debriefed at the end of the Visit 2 regarding the nature of the study and the intervention that they received. Data will be analyzed in a blinded fashion, also to avoid introducing bias. Given the low-risk nature of the study, we do not anticipate a need to break the blind while a subject is enrolled.

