3. STUDY DESIGN

Study design: Single-center, single-blind, pilot randomized controlled trial

Primary outcomes:

- 1) Correlation between physiologic synchrony in patient-provider dyads (GSR or HRV) and improvement in GERD symptom severity.
- 2) Correlation between absolute changes in GSR within subjects over the course of the study visit and subsequent changes in GERD symptom severity.
- 3) Correlation between absolute changes in high frequency HRV within subjects over the course of the study visit and subsequent changes in GERD symptom severity.

Secondary outcomes:

- 1) The difference in the frequency of supportive provider behaviors between the standard and expanded visit groups.
- 2) The difference in the ratings of rapport, engagement, and reciprocity between the standard and expanded visit groups.

Study population:

Men and women age 21-70 with heartburn symptoms 3 or more days per week. We will enroll until we reach 24 completing subjects.

Study location:

The Clinical Research Center (CRC) at Massachusetts General Hospital (MGH), the Benson-Henry Institute (BHI) for Mind Body Medicine, or another MGH location.

Length of subject participation: 2 weeks

Length of study enrollment: 12-14 months

Groups:

- 1) Standard visit (n=8), modeled after an empathic, high quality conventional primary care visit.
- 2) Expanded visit (n=16), modeled after a visit with an integrative medicine provider

Randomization:

The randomization code will be generated by the study statistician as described below (section 4.3). The study will be single-blinded (study providers and the research team will know what the subject is receiving but the subject will not). Randomization will be

Tool Revision History

Version: 11.0

Version Date: 5.8.2020

stratified based on study provider. We anticipate 4 providers each seeing 6 subjects (2 standard visits, 4 expanded visits).

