6.2.5 Telephone check-in

Study coordinators will call enrolled subjects who have completed study visit 1 approximately half-way between the first and second study visits. These telephone check-ins will a) serve as a reminder to participants to complete their daily symptom diary, b) address any participant questions or concerns, and c) remind/confirm participants' second study visit appointment.

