6.2.6 Completion/Final Evaluation

We will attempt to schedule subjects' Visit 2 appointments as close to the 2 week window as possible, but will allow a window of 13-18 days. Visit 2 will be scheduled simultaneously with Visit 1 to help promote adherence to this timeline.

- Current medication List – will be pulled from Epic or the prior visit and verified with the subject by a study team physician.
- Blood draw (optional) – 7.5mL of blood will be obtained by a research nurse in the CRC or other appropriate clinician. Blood will be processed to obtain RNA, and plasma then frozen at -80°C for later omics analyses
- GERD-HRQL - a validated 11 item scale for assessing the impact of GERD symptoms on health-related quality of life [70].
- NIH PROMIS GERD scale – a validated 13 item instrument assessing frequency and severity of GERD symptoms over a 7 day recall period [26].
- GSRS: The Gastrointestinal Symptom Rating Scale is a validated 15 item instrument for measuring the severity of gastrointestinal symptoms [71]. It contains 5 subscales: abdominal pain, reflux syndrome, diarrhea syndrome, indigestion syndrome, and constipation syndrome.
- Current Stress Question – 1 item self-report measure of current stress level on a scale of 0 (no stress) to 10 (extreme stress).
- Perceived Stress Scale (PSS) – a widely used 10 item measure of perceived stress that has been shown to correlate with a variety of different health outcomes [72].
- Adverse events – study staff will ask subjects if they experienced any adverse events and ask about any hospital or emergency room visits since enrollment.
- Daily symptom diary – Identical in content to the baseline symptom diary, this 14 day diary allows subjects to track the frequency and severity of 9 different GERD and dyspepsia-related symptoms on a 5 point scale as well as any medications, supplements, or other products used to help manage symptoms.
- Qualitative interview – a study team member will conduct a semi-structured qualitative interview (see Appendix F) with each subject after the subject has completed questionnaires and prior to the debriefing. These interviews will be audio recorded and will include questions about their perceptions of their interaction with the study provider and with healthcare providers in general and their experience participating in the study.
- GERD handout – an informational handout on GERD and possible treatment approaches will be provided to subjects. See Appendix I.

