9.2 Sample Size and Randomization

This is a pilot study whose aim is to identify features on which to focus in subsequent studies. For the primary outcome, we would consider an observed correlation greater than $r = 0.20$ adequate evidence of a positive association worthy of further investigation. With a sample size of 24 patient-provider dyads, the study will have an 80% probability of obtaining an estimated correlation between physiologic concordance and changes in GERD symptoms (our primary outcome) greater than $r = 0.20$ if the true correlation is at least $\rho = 0.36$. The study will have 80% power to declare the correlation significantly greater than zero based on a two-sided $\alpha = 0.05$ if the true correlation is at least $\rho = 0.54$.

Treatment Assignment Procedures

A randomization scheme will be devised before the start of the study by the study biostatistician who will retain the code and will be responsible for breaking the blind at the end of the study. We do not anticipate a need to break the blind during the study because

Tool Revision History

Version: 11.0

Version Date: 5.8.2020

we are not expecting serious adverse events to occur more frequently in one visit group than another. Randomization will be stratified by provider, with a goal to have 4 providers each see 6 subjects (4 expanded and 2 standard visits each). If a provider cannot commit to this many visits, the study biostatistician may need to adjust the randomization scheme.

The study biostatistician will create numbered envelopes that will indicate which intervention is to be delivered. After a subject has consented to participate in the study, while he or she is completing the baseline questionnaires, immediately prior to the actual visit intervention, the envelope corresponding to the enrolled subject will be opened to reveal which intervention is to be delivered.

If a subject drops or is unable to complete the study, the statistician may need to rebalance the randomization scheme within a stratum.

Subjects will be informed of their “treatment” assignment during a debriefing at the end of the second study visit.

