10.2 Data Management

All paper symptom diaries will be reviewed in real time with subjects to ensure that data can be transferred completely and accurately to electronic form. Such data will be double entered and cross checked as described above. All data (questionnaire, physiologic, video) will be cleaned by study staff and reviewed every 1-2 months by the study PI to ensure accuracy, completeness, and timeliness of subsequent analyses. All biological samples will be labeled with PIDs, logged, tracked, and stored in a securely locked specimen freezer at the BHI.

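### Study staff may know the visit type from Visit 1 onward, so the midpoint call and the staff-run parts of Visit 2 are avoidably unmasked; the likely effect is small and the remedy cheap

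*Combined protocol and SAP*

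**What the plan says.** Two sections set who knows the visit type. Section 3 says that "study providers and the research team will know what the subject is receiving but the subject will not". Section 6.2.3 says: "Study providers and staff will be aware of the study intervention delivered, but only immediately prior to the study visit", and explains the late disclosure as a way "to decrease the potential for introducing bias in how study staff interact with subjects during recruitment and consent". Under section 5.2, "the study provider will open an envelope indicating which visit type he or she is to deliver immediately before conducting the study visit", after which the provider is given the matching script.

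The contacts after the Visit 1 encounter are these:

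- **Midpoint call (6.2.5).** Coordinators telephone about half-way between visits to remind subjects about the diary, to "address any participant questions or concerns", and to confirm the appointment. Section 7.3 adds that unsolicited health concerns are recorded and passed to the PI.
- **Diary review (10.2).** "All paper symptom diaries will be reviewed in real time with subjects".
- **Adverse events (6.2.6, 7.3).** Study staff ask about these at Visit 2.
- **Interview (6.2.6).** After the questionnaires and before the debriefing, "a study team member will conduct a semi-structured qualitative interview".

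No section assigns any of these contacts to someone unaware of the visit type. The safeguards that do exist lie elsewhere: analysis is blinded (6.2.3), video coders are blind to the hypotheses (9.5.2), and the debriefing physician is not the provider who delivered the visit (Précis).

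**The concern.** The protocol accepts that staff who know the arm may behave differently toward subjects, but protects only the period before any outcome exists. The symptom outcomes are all collected later. The trial's premise is that the manner of a clinical contact can change reported GERD symptoms, and sections 4.3 and 5.2 conceal part of the design from subjects because their responses may change if they know what is being studied. An open-ended call by someone who knows the arm fits poorly with that care.

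The primary analysis is a correlation across dyads, not a comparison of arms, but this does not remove the problem. Section 9.1 uses the two visit types deliberately to widen the range of physiologic concordance, and section 9.5.1 states no adjustment for visit type in the Pearson correlations. If staff contact moved symptom reports in one arm, visit type would be related to both variables and some of that shift would appear as correlation. Section 9.2 treats an observed r above 0.20 as worth pursuing, so the practical risk is a false lead.

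**Working it through.** **1. Timing of the call.** Visit 2 falls on day 13 to 18 (6.2.6), so the half-way point is day 6.5 to 9. The diary runs 14 days and the outcome uses the last 7 (9.5.1), that is, from about day 8. The call therefore lands around the start of the outcome window.

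**2. The plan's own figures.** Inputs from 9.2: n = 24, threshold r = 0.20, ρ = 0.36 and ρ = 0.54, two-sided α = 0.05. By Fisher's z, SE = 1/√(24 − 3) = 0.218.

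- P(r > 0.20 | ρ = 0.36) = 1 − Φ[(atanh 0.20 − atanh 0.36)/0.218] = 78.8%.
- Power at ρ = 0.54 = 1 − Φ[1.96 − atanh(0.54)/0.218] = 79.1%.
- Simulation (200,000 runs) gives 80.0% and 80.9%.

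The stated 80% figures reproduce and are not in question.

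**3. Baseline for a false lead.** With ρ = 0, P(r > 0.20) = 1 − Φ(0.2027/0.218) = 17.6%. Simulation gives 17.5%.

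**4. Illustration of an arm-linked shift.** The allocation is 16:8, so p = 2/3 and p(1 − p) = 2/9. Two inputs are assumptions that the documents do not supply:

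- d, the difference between visit types in the physiologic measure, in within-arm SDs.
- b, the shift in reported improvement that staff contact causes in the expanded arm, in within-arm SDs.

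With no association within either arm, the induced correlation is

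ρ* = (2/9)·d·b / √{[1 + (2/9)d²]·[1 + (2/9)b²]}.

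Example, d = 1 and b = 0.5: ρ* = 0.1111/√(1.2222 × 1.0556) = 0.098, and P(r > 0.20) = 1 − Φ[(0.2027 − 0.0981)/0.218] = 31.6%.

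| d | b | ρ* | P(r > 0.20), Fisher | P(r > 0.20), simulated |
|---|---|---|---|---|
| 0.5 | 0.1 | 0.011 | 19.0% | 18.8% |
| 0.5 | 0.2 | 0.021 | 20.3% | 20.3% |
| 0.5 | 0.3 | 0.032 | 21.7% | 21.8% |
| 0.5 | 0.5 | 0.053 | 24.6% | 24.9% |
| 1 | 0.1 | 0.020 | 20.1% | 20.1% |
| 1 | 0.2 | 0.040 | 22.8% | 23.0% |
| 1 | 0.3 | 0.060 | 25.6% | 26.0% |
| 1 | 0.5 | 0.098 | 31.6% | 32.5% |

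Shifts of 0.1 to 0.2 SD give 19–23%. The full range is 19% to about 33%. With b = 0 there is no bias.

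**The case against.** The trial is openly single-blind, subjects do not know that two visit types exist, and the primary outcome is a diary that they fill in themselves. Paper diaries are already written when they are reviewed, and the stated purpose of the review is accurate transfer. The call has the same three purposes in both arms, and nothing suggests that it would be conducted differently by arm. All of this stands, and it makes a small effect the likelier one.

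A reader might go further in four ways that the documents do not support:

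- **That only the provider needs the visit type.** The PI reviews videos for fidelity and feedback (5.1, 9.4), the check after 6 expanded-visit completers (9.4) requires knowledge of the arm, and subjects are told at debriefing which visit they had (6.2.3).
- **That the interview is an unmasked outcome assessment.** It is neither a primary nor a secondary outcome, and it follows the questionnaires, so it cannot alter those symptom scores. What remains is that the interview material itself may be coloured by an interviewer who knows the arm.
- **That section 9.2 contradicts the blinding rules**, because it names a biostatistician "who will retain the code and will be responsible for breaking the blind at the end of the study". That wording is compatible with the blinded analysis promised in 6.2.3.
- **That the table shows a bias.** It shows only what assumed shifts would do. It also sets the genuine effect of visit type on symptoms to zero. Such an effect, which the earlier pilot reported (2.2), would enter the pooled correlation by the same route. That is a question of adjusting for arm, which masking staff would not answer.

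Masking would also be imperfect. Pilot visits averaged 18 against 42 minutes (5.1), and the key-personnel roster lists one research coordinator.

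**Conclusion.** The point holds as a modest design weakness. Sections 3 and 6.2.3 let staff know the visit type from Visit 1, guard only recruitment and consent, and leave the midpoint call and the Visit 2 diary review and adverse-event questions open to people who know the arm. For the primary outcome, the midpoint call is the route that matters most. Adverse-event answers are elicited by staff and so are more directly exposed, but they do not enter the primary correlations.

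The size cannot be derived from the documents. On assumed shifts of 0.1 to 0.5 SD and an assumed physiologic difference of 0.5 to 1 SD, the chance of passing the r > 0.20 threshold without a true within-arm link moves from about 17% to 19–33%, with the lower part of that range more plausible. The sample size and power statements are unaffected. This is a cheap improvement, not an error or an internal contradiction.

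**What to change.** - **5.2 and 6.2.3:** place the matching script inside the sealed envelope and have only the provider open it. Section 9.2 does not say who opens it and should be worded to match. Limit disclosure to the provider, the biostatistician, and the PI or other fidelity reviewer. Anyone so informed should not make the midpoint call or run the Visit 2 assessments that precede debriefing. Amend the statement in section 3 accordingly.
- **6.2.6:** tell the debriefing physician the visit type only once the questionnaires, diary review, adverse-event questions and interview are complete.
- **6.2.5:** give the call a fixed script, identical for both arms, covering the diary reminder, a standard reply to questions and the appointment, with health concerns passed to the PI as section 7.3 already provides.
- **Partial masking:** where existing staffing allows, use a caller who did not attend Visit 1, and record at Visit 2 which type staff believe was delivered.

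The cost is protocol wording, envelope preparation and a short call script. Sample size and analysis do not change. If one coordinator must cover both Visit 1 and follow-up, masking will be limited, because visit length gives a clue to the type; the fixed script is then the part of the change that still protects the call.
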